ACTION Clinical Study Protocol

**A phase II triAl of Cabozantinib for hepaTocellular
carcInoma patients intolerant to sorafenib treatment or
first line treatment different to sorafeNib. (ACTION trial)**

NCT: NCT04316182

Version 4.0 – 15 July 2021

TITLE PAGE

ACTION Clinical Study Protocol

EUDRACT: 2019-004991-20

A phase II triAl of Cabozantinib for hepaTocellular carcinoma patients intolerant to sorafenib treatment or first line treatment different to sorafeNib. (ACTION trial)

| | |
|--------------------|------------------------------|
| Version and status | Version 3.0 – 8 July 2020 |
| | Version 3.1 – 27 August 2020 |
| | Version 4.0 – 15 July 2021 |

Study Sponsor: Fundació Clinic per a la Recerca Biomèdica
Principal Investigators: [name]
Affiliation: BCLC group. Liver Unit. ICMMD. CIBEREHD. IDIBAPS. Hospital Clínic
[name]
[contact]
[contact]
email: [contact]

The study will be conducted in compliance with the protocol, ICH-GCP and any applicable regulatory requirement.

The information provided in this document is strictly confidential and is intended solely for the guidance of the clinical investigation. Reproduction or disclosure of this document – whether in part or full – to parties not associated with the clinical investigation or its use for any other purpose without prior written consent of the sponsor is not permitted.

SYNOPSIS

| Study Title (Full) | |
|--|------------------------------------|
| A phase II trial of Cabozantinib for hepatocellular carcinoma patients intolerant to sorafenib treatment or other First-Line treatment different to sorafenib (ACTION trial) | |
| Related Product | |
| CABOZANTINIB | |
| Indication | |
| Patients with HCC intolerant to sorafenib according to the RESORCE trial definition or those patients who received other first-line treatment. | |
| Phase of Study | Phase IIa |
| Countries | Spain |
| Retrospective or prospective study | Prospective |
| Planned number of sites/ subjects | 7 sites / 40 patients |
| Blinding & Control | non-randomized, non-blinded |
| Study Type and Design | |
| Single arm, interventional, prospective study. | |
| Rationale | |
| 
Cabozantinib, a small molecule directed to vascular endothelial growth factor receptors, MET, and AXL, has shown to significantly improve the overall survival (OS) over placebo in the randomized phase 3 CELESTIAL trial in patients who had up to two lines of prior systemic therapy (including sorafenib) with progression on at least one in comparison to patients who received best supportive care (1).
 
Although cabozantinib shares similar targets with sorafenib/regorafenib, they present different toxicity profile. While the most common grade 3-4 AEs reported for sorafenib were fatigue (4%), diarrhea (8%), hand-foot reaction (8%) and hypertension (2%) (2); the most frequent grade 3-4 AEs for cabozantinib were hand-foot reaction (HFSR) (3.6%), hypertension (3.4%) and elevation of AST (2.6%) (1).
 
In clinical practice, regorafenib, ramucirumab and cabozantinib are approved by EMA as second-line treatment approved by EMA until now (3). However, more than 40% of candidate patients to 2nd line do not meet the RESORCE criteria or REACH-2 trial and are only candidates to cabozantinib treatment. However, we do not have safety data about those patients who are treated with other treatments than sorafenib in first line neither data about the real impact of sorafenib-intolerant patients according to the RESORCE trial definition.
 
For this reason, we propose to explore the role of cabozantinib in patients who were not considered in the CELESTIAL trial.
 | |

| |
|---|
| Primary Study Objective(s) |
| To evaluate the safety profile established by rate of adverse events (AE) with Common Terminology Criteria for Adverse Events (CTCAE)≥3 excluding palmar-plantar erythrodysthesia, rate of related-AEs and rate of death. The rate of AEs leading to treatment discontinuation. |
| Secondary Study Objective(s) |
| Overall survival (OS), objective response rate (ORR), time to progression (TTP), pattern of progression, post-progression survival (PPS), rate of patients who develop new extra-hepatic spread |
| Operational/organizational aspects of the Study |
| Multicenter study conducted by the BCLC in Spain with 7 relevant sites in HCC involved. Some study tasks will be outsourced to a national CRO (regulatory process, EDC system, monitoring plan, analysis, etc.) |
| Study Population |
| Patients with HCC intolerant to sorafenib according to the RESORCE trial definition or those patients who received other first-line treatment. |
| Inclusion Criteria (detailed) |
| 
HCC diagnosed according to criteria of American Association for the Study of Liver Diseases (AASLD) definition in 2010.Intolerant to sorafenib according to RESORCE trial definition or patients who received treatment different to sorafenib as first-Line treatment .The subject has disease that is not amenable to a curative treatment approach (eg, transplant, surgery, radiofrequency ablation)Recovery to ≤ Grade 1 according to (CTCAE) v.5.0. from toxicities related to any prior treatments, unless the adverse events are clinically non-significant and/or stable on supportive therapyRespect the 15 days of first-line treatment washout before starting cabozantinibAge ≥ 18 years old on the day of consentECOG performance status of 0 or 1Adequate hematologic function, based upon meeting the following laboratory criteria within 7 days before starting therapy:
absolute neutrophil count (ANC) ≥ 1200/mm³ (≥ 1.2 x 10⁹/L)platelets ≥ 60,000/mm³ (≥ 60 x 10⁹/L)hemoglobin ≥ 8 g/dL (≥ 80 g/L)Adequate renal function, based upon meeting the following laboratory criteria within 7 days before starting therapy:
Serum creatinine ≤ 1.5 × upper limit of normal or calculated creatinine clearance ≥ 40 mL/min (using the Cockcroft-Gault equation: (140 – age) x weight (kg)/(serum |

| |
|---|
| 
Creatinine x72 [mg/dL]) for males. (For females multiply by 0.85).
 
AND
 
b. Urine protein/creatinine ratio (UPCR) ≤ 1 mg/mg (≤ 113.1 mg/mmol) or 24-hour urine protein < 1 g
 
10. Child-Pugh Score of A
 
11. Total bilirubin ≤ 2 mg/dL (≤ 34.2 µmol/L) within 7 days before starting therapy
 
12. Serum albumin ≥ 2.8 g/dL (≥28 g/L) within 7 days before starting therapy
 
13. Alanine aminotransferase (ALT) and aspartate aminotransferase (AST) <≤ 5.0 upper limit of normal (ULN) within 7 days before starting therapy
 
14. Hemoglobin A1c (HbA1c) ≤ 8% within 28 days before starting therapy (if HbA1c results are unavailable [eg, hemoglobin variant], a fasting serum glucose ≤ 160 mg/dL)
 
15. Antiviral therapy per local standard of care if active hepatitis B (HBV) infection
 
16. Capable of understanding and complying with the protocol requirements and signed informed consent
 
17. Sexually active fertile subjects and their partners must agree to use medically accepted methods of contraception (eg, barrier methods, including male condom, female condom, or diaphragm with spermicidal gel) during the course of the study and for 4 months after the last dose of study treatment
 
18. Female subjects of childbearing potential must not be pregnant at screening. Females of childbearing potential are defined as premenopausal females capable of becoming pregnant (ie, females who have had any evidence of menses in the past 12 months, with the exception of those who had prior hysterectomy). However, women who have been amenorrheic for 12 or more months are still considered to be of childbearing potential if the amenorrhea is possibly due to prior chemotherapy, antiestrogens, ovarian suppression, low body weight, or other reasons.
 
19. Subjects must consent to perform a tumor liver biopsy within 4 weeks before starting cabozantinib, allowing the acquisition of a tumor sample for performance of correlative studies. A formalin-fixed, paraffin embedded (FFPE) tumor tissue block of tumor sample should be stored at local sites for correlative studies. For these biopsies, subjects must have a soft tissue tumor lesion that can be biopsied at acceptable clinical risk, as judged by the investigator. Subjects must consent to the pre-treatment fresh liver biopsy as a condition of protocol participation. If adequate tissue is not obtained during the first procedure then a repeat biopsy should be considered based on the investigator's assessment of clinical risk. However, biopsies at the time of radiological tumor progression are not required to meet eligibility. Tumor biopsy is recommended at the time of tumor progression development. However, patients who develop radiologic tumor progression should have performance status 0/1 and preserved liver function. Finally, patients with symptomatic tumor progression will
 |
|---|

| | |
|---------------------------|--|
| | not be biopsied. |
| Exclusion Criteria | |
| | 
 1. Fibrolamellar carcinoma or mixed hepatocellular cholangiocarcinoma 2. Radiation therapy (eg, I-131 or Y-90) within 4 weeks (2 weeks for radiation for bone metastases or radionuclide treatment within 6 weeks of starting therapy (subject is excluded if there are any clinically relevant ongoing complications from prior radiation therapy) 3. Prior cabozantinib treatment 4. Known brain metastases or cranial epidural disease unless adequately treated with radiotherapy and/or surgery (including radiosurgery) and stable for at least 3 months before starting therapy. Eligible subjects must be without corticosteroid treatment at the time of starting therapy. 5. Concomitant anticoagulation, at therapeutic doses, with anticoagulants such as warfarin or warfarin-related agents, low molecular weight heparin (LMWH), thrombin or coagulation factor X (FXa) inhibitors, or antiplatelet agents (eg, clopidogrel). Low dose aspirin for cardioprotection (per local applicable guidelines), low-dose warfarin (≤ 1 mg/day), and low dose LMWH are permitted. 6. The subject has uncontrolled, significant intercurrent or recent illness including, but not limited to, the following conditions 
 a. Cardiovascular disorders including: 
 i. Symptomatic congestive heart failure, unstable angina pectoris, or serious cardiac arrhythmias ii. Uncontrolled hypertension defined as sustained BP > 150 mm Hg systolic, or 100 mm Hg diastolic despite optimal antihypertensive treatment iii. Stroke (including TIA), myocardial infarction, or another ischemic event within 6 months before starting therapy iv. Thromboembolic event within 3 months before starting therapy. Subjects with thromboses of portal/hepatic vasculature attributed to underlying liver disease and/or liver tumor are eligible b. Gastrointestinal (GI) disorders including those associated with a high risk of perforation or fistula formation: 
 i. Tumors invading the GI tract, active peptic ulcer disease, inflammatory bowel disease (eg, Crohn's disease), diverticulitis, cholecystitis, symptomatic cholangitis or appendicitis, acute pancreatitis or acute obstruction of the pancreatic duct or common bile duct, or gastric outlet obstruction ii. Abdominal fistula, GI perforation, bowel obstruction, intra-abdominal abscess within 6 months before starting therapy iii. Note: Complete healing of an intra-abdominal abscess must be confirmed |

| | |
|--|---|
| | 
prior to starting therapy
 
c. Major surgery within 2 months before starting therapy. Complete healing from major surgery must have occurred 1 month before starting therapy. Complete healing from minor surgery (eg, simple excision, tooth extraction) must have occurred at least 7 days before starting therapy. Subjects with clinically relevant complications from prior surgery are not eligible
 
d. Cavitating pulmonary lesion(s) or endobronchial disease
 
e. Lesion invading a major blood vessel including, but not limited to:, pulmonary artery, or aorta). Subjects with lesions invading the portal vasculature are eligible.
 
f. Clinically significant bleeding risk including the following within 3 months of starting therapy: hematuria, hematemesis, hemoptysis of >0.5 teaspoon (>2.5 mL) of red blood, or other signs indicative of pulmonary hemorrhage, or history of other significant bleeding if not due to reversible external factors
 
g. Other clinically significant disorders such as:
 
 i. Active infection requiring systemic treatment, known infection with human immunodeficiency virus (HIV), or known acquired immunodeficiency syndrome (AIDS)-related illness. Subjects with active hepatitis virus infection controlled with antiviral therapy are eligible. ii. Serious non-healing wound/ulcer/bone fracture iii. Malabsorption syndrome iv. Uncompensated/symptomatic hypothyroidism v. Requirement for hemodialysis or peritoneal dialysis vi. History of solid organ transplantation 
7. Subjects with untreated or incompletely treated varices with bleeding or high risk for bleeding. Subjects treated with adequate endoscopic therapy (according to institutional standards) without any episodes of recurrent GI bleeding requiring transfusion or hospitalization for at least 6 months prior to study entry are eligible.
 
8. Moderate or severe ascites. Note that controlled ascites with stable dose of diuretics in the last month is allowed.
 
9. Corrected QT interval calculated by the Fridericia formula (QTcF) > 500 ms within 7 days before starting therapy
 
Note: If the QTcF is > 500 ms in first ECG, a total of 3 ECGs should be performed. If the average of these 3 consecutive results for QTcF is ≤ 500 ms, the subject meets eligibility in this regard.
 
10. Inability to swallow tablets
 
11. Previously identified allergy or hypersensitivity to components of the study treatment formulations
 
12. Pregnant or lactating females
 
13. Diagnosis of another malignancy within 2 years before starting therapy, except for superficial
 |
|--|---|

| | |
|--|---|
| | 
skin cancers, or localized, low-grade tumors deemed cured and not treated with systemic therapy
 
14. History of allergy to study drug components.
 
15. Prisoners or subjects who are involuntarily incarcerated
 
16. Subjects who are compulsorily detained for treatment of either a psychiatric or physical (eg. infectious disease) illness
 
17. Inability to comply with restrictions and prohibited activities/treatments.
 |
| Test Treatment(s) (Description) | |
| | Cabozantinib will be initiated at full dose (60 mg every day) which will be modified upon development of adverse events according to the manufacturer's recommendations. Treatment will continue until symptomatic tumor progression, unacceptable adverse events, patient decision or death. |
| | Safety reporting |
| 
All AEs that occur after the patient has signed informed consent until at least 30 days after the last dose of the study treatment must be recorded in the CRF.
 
The documentation should be confirmed with a note in the patient's file. An abnormal laboratory result considered clinically significant—e.g. any which causes the patient's withdrawal from the study, requires treatment or causes obvious clinical manifestations, or which is assessed as relevant by the investigator—must be reported as an AE. Each event should be described in detail, together with the start and end dates, severity, relationship to the investigational medicinal product, measures taken and outcome.
 
All actions taken concerning the study treatment to resolve the AE (drug withdrawal, drug suspension, dose reduction, unchanged dose, dose escalation, not applicable, not known) will be documented.
 
Notice to the IECs of all relevant events (e.g. SAEs, Suspected Unexpected Serious Adverse Reactions [SUSARs]) will be given by the sponsor and/or investigator in accordance with the applicable regulations.
 
The processing and communication of all relevant events (SAEs, SUSARs) to the authorities will be carried out by the sponsor in accordance with current legislation.
 
The sponsor will inform all sites of relevant adverse events (e.g. SUSARs) in accordance with current legislation.
 | |
| Standard of Reference/Standard of Truth* | |
| 
Cabozantinib is a second-line treatment approved in HCC. However, in the CELESTIAL trial all patients received sorafenib as first-line treatment.
 | |
| Rationale for selection of a reference treatment | |
| 
In clinical practice, regorafenib, ramucirumab and cabozantinib are approved by EMA as second-line treatment until now (3). More than 40% of candidate patients to 2nd line do not meet the RESORCE criteria or REACH-2 trial and are only candidates to cabozantinib treatment. However, we do not have safety data about those patients who are treated with other treatments of sorafenib in first line
 | |

Sponsor's code: ACTION
EudraCT No: 2019-004991-20
Version: 4.0
Date: 15 July 2021
CONFIDENTIAL

| |
|--|
| 
neither data about the real impact of sorafenib-intolerant patients according to the RESORCE trial definition.
 
For this reason, our aim is to explore the role of cabozantinib in intolerant patients to first-line treatments or patients who received first line treatment different to sorafenib.
 |
|--|

Blinding

Open-label due to the characteristic of the study. All patients will receive cabozantinib orally.

Primary Outcome(s)

Rate of AEs with CTCAE \geq 3 excluding palmar-plantar erythrodysthesia, rate of AEs, rate of related-AEs and rate of death.

Adverse events will be graded following version 5.0 of the CTCAE of the National Cancer Institute, during treatment and 30 days after the last dose before discontinuation.

Secondary Outcome(s)

Time to progression, pattern of progression, overall survival, post-progression survival, progression free survival, rate of patients who develop new extrahepatic spread. ORR

Safety Outcomes

Rate of AE, rate of related-AEs and rate of death.

Adverse events will be graded following version 5.0 of the CTCAE of the National Cancer Institute, during treatment and 30 days after the last dose.

Visit schedule

Baseline evaluation and Follow-up included:

All patients will be biopsied before starting cabozantinib. If the patient has a previous tissue sample, that material will be analyzed. However, this does not exclude the need to perform a biopsy within the month after initiation and at the time of developing radiologic tumor progression.

Follow-up period

Follow-up will include clinical and laboratory assessment every 2 weeks within the first 2 month, then every 4 weeks, tumor evaluation at week 4 and every 8 weeks thereafter. In addition, unscheduled visits will be made should they be needed (adverse events or symptoms). At each time point that the dose is changed we will perform a blood extraction to determine serum biomarkers. Moreover, a second extraction will be done 7 days after modifying the cabozantinib dose. Adverse events will be graded following version 5.0 of the CTCAE of the National Cancer Institute, during treatment and 30 days after the last dose. Tumor evaluation during follow-up will be evaluated by CT-scan. Response and TP will be defined according to the RECIST criteria v1.1. Outcomes will be measured from the date of starting cabozantinib until the date of death regardless of cause of death. TTP will be defined as the time from the starting date of cabozantinib to disease progression (according to RECISTv1.1). PPS will be measured from the date of detecting progression at radiology until the date of death or

last follow-up. Assessment will be done by radiologists in each center and then a central revision by radiologists with more than 10 years of experience in HCC and blinded to the evolution and outcome of the patients. Disease-control rate (DCR) will be defined as the percentage of patients who had a best-response rating of complete response (CR), partial response (PR) or stable disease (SD) (according to RECIST and BCLC-RECIST) maintained for at least 28 days after the first demonstration of best-response rating as per independent radiologic review.

Statistical & Analytical Plan and Methodology

The study will be analyzed using standard statistical methods to estimate rates and 95%CI (for ORR and other binary variables) by means of the Clopper-Pearson exact method, and the Kaplan-Meier method to describe the survival functions and the median and [95%CI]. A Statistical Analysis Plan, which will include all details regarding all analyses, the interim method, the handling of missing data and any plan for the analysis, will be finalized before the initiation of the study recruitment.

The sample size calculation will be triggered by the primary outcome, i.e, the rate of adverse events (AE) with CTCAE≥3 excluding palmar-plantar erythrodysthesia (critical AEs). The expected rate for this outcome was 56% in this population. The Simon's two-stage optimal design will be used to test the alternative hypothesis that with cabozantinib the rate of critical AEs will be reduced at least to 32.5% against the null hypothesis of 56%. In the first stage, 14 patients will be accrued and if there are 8 or more critical AES in these 14 patients, the study will be stopped for futility. Otherwise, 26 additional patients will be accrued for a total of 40. The null hypothesis will be rejected if 23 or fewer critical AEs are observed in 40 patients. This design yields a type I error rate of 2.5% one-sided and power of 80% when the true response rate is 67.5%.

Planned Study Timelines:

1. Enrolment rate (patients per month): 3
2. Planned estimate of treatment(s) duration: **24months**
3. Submission date to health authority/ethics: Jan 2020
4. Start of subject enrolment: March 2020
5. End of Subject enrolment: Jul 2022
6. All patients completed: **Oct 2023**
7. End of Study: Jan 2024
8. Report: **Q2-Q3 2024**
9. Planned publication/presentation: Q1 2025

TABLE OF CONTENTS.

| | |
|--|-----------|
| TITLE PAGE | 1 |
| SYNOPSIS | 2 |
| 1. INTRODUCTION | 13 |
| 1.1 HEPATOCELLULAR CARCINOMA | 13 |
| 1.2 CABOZANTINIB: BACKGROUND | 13 |
| 1.2.1 PHARMACOLOGY AND PHARMACOKINETICS..... | 13 |
| 1.2.2 CABOZANTINIB SAFETY SUMMARY IN PATIENTS WITH HEPATOCELLULAR CARCINOMA..... | 16 |
| 1.2.3 SUMMARY OF CABOZANTINIB CLINICAL ACTIVITY IN HEPATOCELLULAR CARCINOMA..... | 16 |
| 1.2.4 RATIONALE FOR THE CURRENT STUDY | 17 |
| 1.2.4.1 TREATMENT SCHEDULE | 17 |
| 2. STUDY OBJECTIVES..... | 17 |
| 3. ETHICAL CONSIDERATIONS..... | 17 |
| 3.1 GOOD CLINICAL PRACTICE | 17 |
| 3.2 INSTITUTIONAL REVIEW BOARD/INDEPENDENT ETHICS COMMITTEE | 18 |
| 3.3 INFORMED CONSENT..... | 18 |
| 4. STUDY DESIGN AND PLAN | 19 |
| 4.1 TREATMENT PLAN..... | 19 |
| 4.1.1 SCREENING PHASE | 19 |
| 4.1.2 CABOZANTINIB..... | 20 |
| 4.1.3 END OF THE STUDY | 20 |
| 4.1.4 DISCONTINUATION OF CABOZANTINIB..... | 21 |
| 4.1.5 POST STUDY DRUG STUDY FOLLOW-UP..... | 21 |
| 4.1.6 WITHDRAWAL OF CONSENT | 21 |
| 4.1.7 LOST TO FOLLOW-UP | 22 |
| 5. PATIENT POPULATION..... | 22 |
| 5.1 INCLUSION CRITERIA..... | 22 |
| 5.1.1 SIGNED WRITTEN INFORMED CONSENT | 22 |
| 5.1.2 TARGET POPULATION | 22 |

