4.1 TREATMENT PLAN

4.1.1 SCREENING PHASE

Study entry is defined as the date that the Informed Consent has been signed by the patient. No patient may undergo any screening procedures that are not considered standard of care to assess his/her eligibility to receive protocol treatment, or commence protocol treatment, prior to signing the informed consent form. The time period between study entry and the commencement of protocol treatment is not to exceed 28 days. Patients may only commence protocol treatment after all eligibility criteria have been confirmed. After signing the informed consent and upon documentation of eligibility, the patient will be allocated with an enrolment number and registered in an enrolment log. The patient identification number will be multi-digit, to represent the investigational site and an enrolment number that will be unique to each subject. All patients referred for possible participation in this study must be assessed at screening to confirm the patient's eligibility. All documentation supports the inclusion and exclusion criteria and screening investigation results are to be retained by the Investigator and made available for monitoring by the study

Sponsor including source data verification. All patients assessed as ineligible to be enrolled in the study after study entry are considered screening failures. The investigator will have their initials recorded on the Patient Screening Log and no further data will be collected for these patients. The Patient Screening Log will include the reason(s) for the patient not meeting the eligibility criteria and will be maintained by the site and copies retained by the study Sponsor. Patient who withdrew consent after study entry but before treatment for any reason will be considered screening failures and should be registered in the screening log.

The study monitor should be contacted in the event of any query or uncertainty relating to a patient's eligibility to receive protocol treatment:

[name]

BCLC group, Liver Unit, Hospital Clinic de Barcelona
Email: [contact]
[contact];
[contact]

[name]

BCLC group, Liver Unit, Hospital Clinic de Barcelona
Email: [contact]
[contact];
[contact]

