| Study procedures and examinations | | | | | | | |
| Physical examination | x | x | x | * | x | x | |
| ECOG performance status | x | x | x | * | x | x | |
| 12-lead ECG ⁴ | x | | | | | x | |
| Vital signs ⁵ | x | x | x | * | x | x | |
| Assessment of AEs/SAEs | x | x | x | * | x | x | |
| Concomitant medications | x | x | x | * | x | x | |
| Diet and gut microbiota | x | | | | | | |
| | | | | | | | |
| Laboratory tests | | | | | | | |
| Serum chemistry ⁶ | x | x | x | * | x | x | |
| Hematology ⁷ | x | x | x | * | x | x | |
| Coagulation (PT, INR, PTT) | x | x | x | * | x | x | |
| HBsAg and HBsAb, HBcAb and HCV Ab; HBeAg and HBeAb, HBV DNA and HDV RNA and HDV Ab(HBV+ subjects only); HCV RNA (HCV+ subjects only) | x | | | | | x | |
| Thyroid function tests (TSH, free T3, free T4) | x | | | | | | |
| Urinalysis | x | x | x | * | | x | |
| Urine or serum pregnancy test (WOCBP) | x | | | | | | |
| | | | | | | | |
| Other procedures⁸ | | | | | | | |
| Other laboratory blood tests and assays ⁹ | | x | x Only in C1 | | x | | |
| Other liver tissue analysis ¹⁰ | x | | | * | x | | |
| Patient-reported Quality of Life (EQ-5D, EORTC-QLQ C30, EORTC-HCC18 and FACT-Hep) ¹¹ | | x | | | x | x | |
| Other stool tests and assays ¹² Day 1 | | x | | | | x | |

Sponsor's code: ACTION
EudraCT No: 2019-004991-20
Version: 4.0
Date: 15 July 2021
CONFIDENTIAL

Cycle 4 and in case of OR or PD

EOT: End of Treatment; **OR:** Objective Response; **PD:** Progressive Disease

¹ The time period between study entry and the commencement of protocol treatment is not to exceed 28 days.

² Follow-up visits could be on-site or phone visits after the last visit and will include survival data and liver cirrhosis complications evaluation every 3 months. If the patient does not start any other treatment after end of treatment, radiologic follow-up with the same scheduled will be preferred. Laboratory tests will be performed at the discretion of the treating investigator until death or the end of the study.

³ A biopsy will be performed at the time of progression whenever possible.

⁴ Note: The ECG should be performed within the 7 days prior the randomization. If the QTcF is > 500 ms in first ECG, a total of 3 ECGs should be performed. If the average of these 3 consecutive results for QTcF is ≤ 500 ms, the subject meets eligibility in this regard.

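### The pregnancy test is scheduled once, at screening, with no day window before first dose and none expressly scheduled on treatment or at end of treatment

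*Protocol*

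**What the plan says.** **Eligibility.** Inclusion criterion 18 (Synopsis, repeated in section 5.1.2) reads "Female subjects of childbearing potential must not be pregnant at screening". It gives no number of days before first dose. Exclusion criterion 12 (Synopsis, repeated in 5.2.1) is "Pregnant or lactating females", with no time reference.

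**Timing of first dose.** Section 4.1.1 defines study entry as the date of signed consent and says "The time period between study entry and the commencement of protocol treatment is not to exceed 28 days". It also says "Patients may only commence protocol treatment after all eligibility criteria have been confirmed".

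**Schedule.** Table 5 of the protocol and the flow chart in SAP 7.7 each mark the pregnancy test once, under Screening. The columns for cycle visits, first radiologic progression, EOT and follow-up are blank in that row. Section 7.2.6.4 lists the test without attaching a visit. It closes by waiving Cycle 1 Day 1 laboratory work done within the preceding 7 days. Section 7.1 places laboratory evaluation on Day 1 of every cycle and Day 15 of Cycles 1 and 2, again without naming the test.

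**Other safeguards.** Contraception is required during the study and for 4 months after the last dose, and refusing it is a reason to stop drug (6.1.6). Pregnancy is a listed reason to stop (4.1.4, 6.1.6). Women are told to report a pregnancy at once (8.1.4.1), and unscheduled laboratory tests are available for adverse events or symptoms (7.1).

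**The concern.** The protocol treats pregnancy as an exclusion and as a reason to stop drug, but dates the test less tightly than most of its other laboratory criteria. If a site follows Table 5 as marked, a woman who conceives between the screening test and first dose could start cabozantinib with a negative result on file. A woman who conceives later could stay on drug until she reports the pregnancy or a visit brings it to light.

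Two statements in the protocol suggest that clinical recognition could be slow. Criterion 18 counts some women with 12 or more months of amenorrhea as of childbearing potential, and in them a missed period gives no warning. Section 1.2.2 reports fatigue in 45%, nausea in 31% and vomiting in 26% of patients in the phase 3 trial of cabozantinib, so symptoms of early pregnancy could be put down to the drug.

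What is at stake is the safety of individual women and of a fetus. No estimate, error rate or decision rule is affected.

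**Working it through.** The plan states no figure to reproduce. The check compares texts and adds a little arithmetic on test age and workload.

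**Step 1. Read the schedule.** In both Table 5 and SAP 7.7 the count of marked pregnancy tests is: screening 1, on treatment 0, EOT 0, follow-up 0. Nearby rows (urinalysis, hepatitis serology) keep their EOT marks and the two documents agree, so the blanks do not look like a fault in reading the table.

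**Step 2. Compare the windows before first dose.**

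| Criterion | Window before first dose |
|---|---|
| Hematology; renal function, including urine protein | 7 days |
| Bilirubin, albumin, ALT/AST | 7 days |
| QTcF ("Corrected QT interval calculated by the Fridericia formula (QTcF) > 500 ms within 7 days before starting therapy") | 7 days |
| HbA1c | 28 days |
| Pregnancy (criterion 18) | none stated; at screening only |

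Blood and urine are therefore already needed inside a 7-day window.

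**Step 3. Oldest possible test at first dose.** Assume the test is done no earlier than the day of consent.

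- As Table 5 is marked: up to 28 days.
- If the closing sentence of 7.2.6.4 is read as requiring a repeat: up to 7 days.
- Removed by an explicit 7-day rule: 28 − 7 = up to 21 days under the first reading, and nothing under the second.

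**Step 4. Test age on treatment.** Treatment duration is not fixed, so assume n = 3, 6 or 12 cycles of 28 days. The age of the single test at the end of cycle n is at most 28 + 28n days:

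- n = 3: 28 + 84 = 112 days
- n = 6: 28 + 168 = 196 days
- n = 12: 28 + 336 = 364 days

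With a test on Day 1 of each cycle the interval would be 28 days nominally. With the ±72-hour visit windows it would be at most 28 + 3 + 3 = 34 days.

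**Step 5. Workload.** Tests on Day 1 of Cycles 2 to n plus one at EOT come to (n − 1) + 1 = n per woman: 3, 6 or 12. The pre-dose rule adds 0 or 1. The range is 3 to 13 per woman over 3 to 12 cycles. The documents do not say how many women of childbearing potential are expected. Assuming 0 to 2 of the 40 patients, the total is between 0 and 2 × 13 = 26 added tests. Table 5 already collects serum and urine on Day 1 and at EOT, so no visit is added.

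These figures describe test age and workload. They do not measure the risk of pregnancy.

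**The case against.** The strongest reply concerns the period before first dose. Exclusion 12 is not limited to screening, and treatment may start only once eligibility is confirmed. The last sentence of 7.2.6.4 follows a list that includes the pregnancy test, so its ordinary reading could be that a test older than 7 days is repeated at Cycle 1 Day 1. The Day 1 laboratory line in 7.1 points the same way. Table 5 is also not exhaustive: it omits HbA1c, which is an eligibility test, and the weekly blood pressure checks in 7.2.6.1. A blank cell is therefore weaker evidence than it first appears.

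Much of this stands. It makes the pre-dose position ambiguous rather than plainly deficient. It does not settle the matter: neither exclusion 12 nor the confirmation rule dates the test, and neither 7.1 nor the closing sentence of 7.2.6.4 names it. Thyroid tests, on the same 7.2.6.4 list, are also marked at screening only. Two sites could reasonably act differently.

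A second reply is that repeat testing on treatment is a clinical choice and that no rule in the protocol is broken by its absence. That also stands, so the interval should be left to the clinical team.

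A reader might go further and infer that every existing safeguard works only once a pregnancy is suspected. The documents do not support that. Contraception is preventive and needs no suspicion, and examinations and adverse event review take place at scheduled visits regardless. The narrower statement holds: no scheduled test looks for a pregnancy after screening.

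A reader might also take 28 days as the usual age of the test at first dose. It is an outer bound counted from consent. Nothing shows that sites would test at the earliest date, and the other blood work has to be done within 7 days anyway.

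**Conclusion.** The point holds as a cheap improvement to patient safety. Followed as marked, the schedule allows first dose on a pregnancy test up to 28 days old, and 7.2.6.4 leaves it unclear whether an older test must be repeated. No test is expressly scheduled on treatment or at EOT. Contraception reduces the risk, but detecting a pregnancy depends on self-report, clinical visits or tests prompted by symptoms.

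The pre-dose part is the firmer of the two, because the protocol already uses a 7-day window for most of its laboratory criteria. The on-treatment part is a low-cost suggestion whose frequency is a clinical decision.

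The conclusion rests on both schedules being read as printed and on the test being done no earlier than consent. The cycle counts and the 0 to 2 women are assumptions, and at the lower end no woman is affected. Few cases limits how often this could matter, but an unrecognised fetal exposure would still be serious for those concerned. The sample size, error rates and primary estimate are unchanged.

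**What to change.** 1. In inclusion criterion 18 (Synopsis and 5.1.2), require a negative urine or serum pregnancy test within 7 days before first dose in women of childbearing potential. Show the same window in Table 5 and SAP 7.7.
2. In Table 5 and SAP 7.7, add a pregnancy test on urine or blood already collected at on-treatment visits, at an interval set by the clinical team (for example Day 1 of each cycle), and one at EOT.

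The cost is a wording and schedule amendment, 0 or 1 extra test per woman before first dose and, if Day 1 testing is chosen, 3 to 12 more over 3 to 12 cycles. The tests are inexpensive, use samples already taken and probably concern very few women. If the team prefers a longer interval on treatment, item 1 should still be adopted.
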